11.2.2 Secondary Objectives

The secondary objectives and endpoints for this module are listed in [Table 13](#). See Section 3 of the core protocol for all other secondary objectives.

Table 13 Secondary Objectives - Module 1

Objectives	Estimand description
Complete Response Rate (CR+CR_i)	

Table 13 Secondary Objectives - Module 1

Objectives	Estimand description

 To estimate the preliminary antitumor activity of AZD0466 by assessment of Complete response rate (CR+CR_i) in patients with advanced haematological malignancies 	
 Complete response rate (CR+CR_i) is defined as the proportion of patients who have a complete remission (CR) or incomplete haematological response (CR_i), as determined by criteria described in Appendix J, Appendix K and Appendix O. The analysis will include all dosed patients as intended. Data obtained from first dose up until progression, or the last evaluable assessment in the absence of progression, will be included in the assessment of CR+CR_i, regardless of whether the patient withdraws from study treatment. Patients who go off treatment without a response or progression, receive a subsequent therapy, and then respond will not be included as responders in this evaluation. The measure of interest is the estimate of CR+CR_i.
Time to Response (TTR)	

 To estimate the preliminary antitumor activity of AZD0466 by assessment of time to complete response (TTR) in patients advanced haematological malignancies 	
 Time to response is defined as the time from date of first dose until the date of first documented CR or CR_i. The analysis will include all dosed patients as intended, who have a complete remission. Patients who go off study treatment without a clinical response and receive a subsequent therapy and then respond will not be included. The measure of interest is median TTR.
Duration of Response (DoR)	

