8.5 Analysis Sets

Details of the analysis sets are presented in [Table 5](#).

Table 5 Analysis Sets – Module 1

Population/Analysis set	Description
Screened	All patients that signed the informed consent form (ICF)
Safety	All patients who received at least one dose of AZD0466
Intention-to-treat	All patients who received at least one dose of AZD0466
Evaluable for Response	All patients who have received at least 3 doses of AZD0466 at the target dose level in Cycle 1
DLT-evaluable	
Patients enrolled in the dose-escalation part of Module 1 that have received at least 3 doses of AZD0466 at the target dose level (75% of target doses from Day 8 to Day 29 in Cycle 1) and have completed the safety follow-up through the 35-day DLT evaluation period
 
Or
 
Have experienced a DLT during the 35-day DLT evaluation period in Cycle 1.

Pharmacokinetics	Dosed patients with at least one reportable plasma concentration and no important AEs or protocol deviations that may impact PK

A summary on which analysis set will be used for each outcome variable is provided in [Table 6](#).

Table 6 Summary of outcome variables and analysis sets

Outcome variable	Analysis Set
Study Population/Demography Data	
Disposition	Enrolled
Demography and baseline characteristics	Safety
Important protocol deviations	Safety
Medical History	Safety
Prior/Concomitant Medication	Safety
Safety data	
Exposure	Safety
Adverse Events	Safety
Laboratory measurements	Safety
Vital Signs/ECG/Physical examination	Safety
ECOG PS	Safety
DLTs	DLT-evaluable
Efficacy Data	
CR rate	Evaluable for response; Intention-to-treat
TTR	Evaluable for response
DoR	Evaluable for response
OS	Intention-to-treat
ORR	Evaluable for response; Intention-to-treat
Pharmacokinetics	
Pharmacokinetic variables	PK

CR complete response; DLT dose-limiting toxicity; DoR duration of response; ECOG PS Eastern Co-operative Oncology Group performance status; OS overall survival; PK pharmacokinetic.

The number of enrolled patients included/excluded from each of the analysis sets will be summarized. Patients and data excluded from each analysis set will be listed with the reason for exclusion.

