8.10.2 Primary Efficacy Endpoints

8.10.2.1 Complete Response (CR+CRi) Rate

Complete response rate (CR+CRi) for AML and ALL patients is defined as the proportion of patients with best response as complete remission (CR) or incomplete haematological response (CRi), as determined by criteria described in Section 3.2.1 and in Appendix J and Appendix K in the study protocol. Any treated patient who has not satisfied the criteria for CR or CRi will be treated as a non-responder for this analysis.

Data obtained from first dose up until treatment failure or disease progression, or the last evaluable assessment in the absence of treatment failure or disease progression, will be included in the assessment of CR+CRi, regardless of whether the patient withdrew from study treatment.

The complete response rate will be presented along with all remaining response categories, as defined in Section 3.2.1 by means of the proportion (%).

The analyses will include all patients from the Evaluable for Response analysis set. Patients who went off treatment without a response or who received a subsequent therapy after treatment failure or disease progression, and then respond will not be included as responders in this evaluation.

Secondarily, the analyses will be repeated for the Intention-to-treat analysis set, for that the denominators for the calculation of percentages will refer to the number of patients in the Intention-to-treat analysis set. Patients who are not evaluable for response analysis will not be assigned to a response category and frequencies for missing data items will not be presented.

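### Two response rules in SAP 8.10.2.1 depart from the protocol and could leave a documented CR or CRi uncounted

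*SAP*

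**What the plan says.** SAP 8.10.2.1 defines the CR+CRi rate for AML and ALL patients in Module 1 Part A. It uses data from first dose until treatment failure or progression, "regardless of whether the patient withdrew from study treatment". The rate is calculated first on the Evaluable for Response set and then, secondarily, on the ITT set, which is all dosed patients.

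Two rules in that section matter here.

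(a) Late responses. "Patients who went off treatment without a response or who received a subsequent therapy after treatment failure or disease progression, and then respond" are not counted as responders. The matching rule in protocol 11.2.2, Table 13, reads: "Patients who go off treatment without a response or progression, receive a subsequent therapy, and then respond will not be included as responders". SAP 6.2 carries the protocol rule over.

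(b) The ITT repeat. Here "the denominators for the calculation of percentages will refer to the number of patients in the Intention-to-treat analysis set", yet "Patients who are not evaluable for response analysis will not be assigned to a response category", and missing items get no frequency row. The only definition of evaluability for response is in SAP 8.5 (and protocol Table 21): "All patients who have received at least 3 doses of AZD0466 at the target dose level in Cycle 1". For the population of this endpoint, protocol Table 13 says: "The analysis will include all dosed patients as intended".

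**The concern.** Both rules can turn a documented responder into a non-responder for a reason that the protocol does not recognise.

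Under (a), stopping treatment without a response is enough. The protocol needs a further event, a subsequent therapy, which is what would make the late response hard to attribute to AZD0466. Without that event the protocol counts the response.

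Under (b), evaluability is a count of Cycle 1 doses and does not depend on whether a marrow was assessed. An ITT repeat should show what happens when every dosed patient is classified. If patients below the dose count can never be classified, the repeat only puts the evaluable-set numerator over a larger denominator.

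At stake is the accuracy of a secondary activity estimate and its agreement with the protocol's definition. No test or planned decision rests on it.

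**Working it through.** **Rule (a), text against text.**

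- Protocol Table 13 and SAP 6.2 join three conditions: off treatment without response or progression, and a subsequent therapy received, and then a response.
- SAP 8.10.2.1 gives two alternatives: off treatment without a response, *or* a subsequent therapy after failure or progression; in either case followed by a response.
- Test case: a patient stops without a response, receives nothing further, does not progress, and then meets CR or CRi. The protocol and SAP 6.2 count this patient. SAP 8.10.2.1 does not.
- Attaching the later response to both alternatives does not help, because the first alternative still needs no new therapy.
- The same SAP section also says that data count whether or not the patient withdrew from treatment, so it contradicts itself.

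The case can arise. Protocol 7.1 keeps discontinued patients in follow-up. A marrow at the end-of-treatment visit is required unless one was done in the preceding 21 days (Table 17). SAP 3.2.1 includes unscheduled assessments.

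**Rule (b), text against text.**

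- Cycle 1 target doses fall on Days 8, 15, 22 and 29. A patient with fewer than three of these is not evaluable.
- Protocol Table 7 allows holds of up to 21 days followed by a restart, while the Day 30 marrow stays scheduled (protocol 11.6.1.3). A patient who misses Days 15 and 22 has 4 − 2 = 2 target doses, may still be on treatment, and can have an assessed marrow.
- If that patient reaches CR or CRi, protocol Table 13 includes the patient. Protocol 11.7.6 makes a treated patient a non-responder only if CR or CRi was not met, and SAP 8.10.2.1 itself repeats that rule. SAP 3.2.1.1 and 3.2.1.2 have the investigator assign a category regardless of discontinuation.
- Read on the SAP 8.5 definition, the rule in (b) assigns none.

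SAP section 13 says that protocol 11.7.6 will be applied to Part A if data allow, and lists neither departure as a change.

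**Size, as illustration only.** The protocol enrols up to 48 patients to obtain about 36 DLT-evaluable, and its summary of changes gives a 25% fallout. This reproduces: 36 / (1 − 0.25) = 48, leaving 48 − 36 = 12. The documents give no response-evaluable share, so the DLT-evaluable share is borrowed as an assumption.

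Under rule (b), the ITT rate equals the evaluable-set rate × 36/48 = 0.75, whatever happens in the other 12. Assume 7 responders among the 36 (19.4%), and let k be the documented responders outside the evaluable set. The documents do not give k.

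| k | ITT rate under SAP rule (b) | ITT rate counting every documented responder |
|---|---|---|
| 0 | 7/48 = 14.6% | 7/48 = 14.6% |
| 1 | 7/48 = 14.6% | 8/48 = 16.7% |
| 2 | 7/48 = 14.6% | 9/48 = 18.8% |
| 3 | 7/48 = 14.6% | 10/48 = 20.8% |

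Each uncounted responder costs 1/48 = 2.1 points, or 1/40 = 2.5 points with the enrolment of 40 still printed in SAP 7.1. For scale, the exact 95% interval for 7/48 is 6.1% to 27.8%.

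**The case against.** **Rule (b) has a second reading.** The sentence does not use the name of the Evaluable for Response set, and it goes on to speak of missing items. It may mean only patients with no response assessment. On that reading no documented responder is lost. This stands as a possibility, but the SAP nowhere defines evaluability that way, so the sentence needs clarifying in any case.

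**Rule (b) does not touch the evaluable-set analysis.** Protocol 9.5 places response endpoints on the evaluable set, and the SAP puts that set first. This stands: (b) concerns only the secondary ITT repeat. Rule (a) applies to both.

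**The right wording for (a) is already in SAP 6.2.** True, but the SAP then holds two incompatible rules, and the one in the analysis section is the one likely to be programmed. It is also fair that no marrow is scheduled between the end-of-treatment visit and progression, so first responses after stopping should be uncommon.

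**A reader might infer that a quarter of dosed patients, 12 of 48, lose the chance to be counted, and that the ITT rate is materially biased.** The documents do not support this:

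- The 25% is attributed to disease progression, and the response window closes at progression, so most of those patients would be non-responders under any rule.
- It describes DLT-evaluability, which is a different set. A patient with a DLT after one dose is DLT-evaluable but not evaluable for response.
- The 48 is a planned ceiling. It leaves out the 18 backfill patients and may include MDS patients, for whom this rate is not defined. Recruitment stopped on 16 June 2023 and the study was terminated. The number dosed is not given.

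**Nor can one argue that CR and CRi both wait for count recovery after dosing stops.** CRi is defined by incomplete recovery in Appendices J and K.

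**Little depends on the rate.** Response-related data are listed for every ITT patient (SAP 8.10), no hypothesis is tested, and Part B, where response rates would have guided decisions, was not initiated. This limits the consequence but does not remove the conflict.

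**Conclusion.** The point holds as a conflict of rules with an effect of unknown size. Rule (a) plainly contradicts protocol Table 13, SAP 6.2 and a sentence in its own section. Rule (b) is a defect on the only definition of evaluability that the SAP gives, and at best an ambiguity. It is confined to the secondary ITT repeat.

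Any bias in the CR+CRi rate is downward. The number of patients affected is not in the documents and may be zero. The figure of about 2 points per lost responder assumes 48 dosed patients and serves only for scale. The analysis is descriptive, so the matter is one of correct classification and agreement with the protocol. The documents do not establish that any real responder has been lost.

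**What to change.** 1. In SAP 8.10.2.1, replace the late-response sentence with the condition in protocol Table 13 and SAP 6.2, so that a response is excluded only if it was first documented after the start of subsequent anticancer therapy. The existing cut-off at treatment failure or progression stays.
2. In the ITT table, classify every dosed AML or ALL patient by documented best response. Add a row for patients not evaluable or not assessed, counted as non-response only where no CR or CRi was documented. The categories then add to the ITT total, and the second reading of the sentence no longer matters.

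The cost is two sentences and one table row, with no new data. If the tables already exist, check the response listings for patients with fewer than three Cycle 1 target doses and for first responses after the end of treatment. Then report any patient whose classification changes.

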8.10.2.2 Overall Survival (OS)

The number of deaths will be summarised. The number of censored patients, and reason for censoring, will also be summarised.

OS will be summarised using the Kaplan-Meier technique. The quartiles (Q1, median, and Q3) of OS will be summarised, including 95% CIs. The percentage of patients survival rate at 3, 6, 9 and 12 months along with the 95% CI will be presented. The median (range) duration of follow-up among censored subjects (months) will also be presented.

8.11 Pharmacokinetics

For the definitions of handling, calculation and presentation of pharmacokinetic concentrations and parameters refer to Section 4.13. For PK parameters and calculations supporting Module 1, see section 7.2.2. There are no formal statistics planned for Module 1 PK results; these will be summarized descriptively by cohort, and sampling interval, or other appropriate subsetting.

Amount and cumulative amount of AZD4320 excreted will be listed and summarized by urine collection intervals per day of infusion during cycle 1, as appropriate. In addition, individual urine PK parameters will be listed.

8.12 Safety and Tolerability Evaluation

Safety, tolerability and DLT data will be listed and summarised as defined by the current AZ standards (oncology early phase study outputs).

Safety analysis set will be used for all safety and tolerability analyses. All listings and tables, other than those to assess DLTs during Cycle 1 in Part A, will be based on the safety analysis set. To describe the DLTs during Cycle 1 in Part A, the DLT-evaluable analysis set will be used.

Part A includes the AEs, AESIs, laboratory data, vital signs, ECG, LVEF (by MUGA/ MRI/ ECHO) as safety assessments. The listings and tables of all safety data for Part A will be created as described in this section. In addition, for Part A, DLTs will be listed and summarised; MTD (if determined) will be reported.

8.12.1 Exposure and treatment administration

For the calculation and presentation of exposure and treatment administration refer to Section 4.14.1.

8.12.2 Dose limiting toxicities (DLTs)

Refer to Section 4.14.2.

8.12.3 Definition of Maximum Tolerated Dose and Definition of Recommended Phase II Dose

Refer to Section 4.14.3.

8.12.4 Adverse Events

Refer to Section 4.14.4.

8.12.5 Deaths

Refer to Section [4.14.5](#).

8.12.6 Clinical Laboratory Evaluation

Refer to Section [4.14.6](#).

8.12.7 Vital Signs

Refer to Section [4.14.7](#).

8.12.8 ECGs

Refer to Section [4.14.8](#).

8.12.9 LVEF

Refer to Section [4.14.9](#).

8.12.10 Eastern Cooperative Oncology Group performance status (ECOG PS)

Refer to Section [4.14.10](#).

8.12.11 Tumour lysis syndrome (TLS)

Refer to Section [4.14.11](#).

8.13 Determination of Sample Size**8.13.1.1 AZD0466 Monotherapy Escalation - Part A**

The primary objective of Part A is to identify the MTD and RP2D of AZD0466 monotherapy. In Part A, 3 to 12 DLT-evaluable patients may be treated in each dose level using an mTPI-2 design ([Guo et al 2017](#)) permitting up to a maximum of 30 DLT-evaluable patients for dose exploration. In addition, any tolerated dose level may be expanded at the discretion of the sponsor in discussion with the SRC to include up to a total of 18 patients for further evaluation of PK, PD, safety, or biological efficacy. Up to a total of 58 patients will be enrolled to yield a maximum of 30 DLT-evaluable patients and 18 patients for further exploration in Part A. This limits the number of patients exposed to AZD0466 consistent with the expected safety profiles of the study treatment, but includes sufficient patients to explore safety of the treatment, PK and effects on pharmacodynamic biomarkers, and to collect preliminary efficacy data.

8.14 Interim Analyses (Not applicable)

9 INTRODUCTION – Module 2

Module 2 will be initiated by the SRC (Appendix A5 of the study protocol) after a tolerated dose of AZD0466 has been determined in Module 1. This is a DDI study that will evaluate AZD0466 with voriconazole, a strong inhibitor of CYP3A4.

For further general study information refer to Section 1.

10 STUDY OBJECTIVES - Module 2

The core objectives and endpoints for the study are listed in Sections 2.1, 2.2 and 2.3; additional secondary endpoints for Module 2 are listed in Section 10.1

10.1 Secondary Objectives

Objectives	Endpoints/Variables
To assess the drug-drug interaction potential between AZD0466 and the azole antifungal voriconazole.	AUC (AUC0-72 and AUClast) and C _{max} of AZD4320 (total and released) after administration of AZD0466 alone and in combination with voriconazole

11 INVESTIGATIONAL PLAN - Module 2

[figure not shown]
11.1 Overall Study Design

Module 2, a Phase I DDI study of AZD0466 and the azole antifungal agent voriconazole, will be conducted in patients with AML or ALL to determine the effect of voriconazole on the PK of AZD0466. This module will be conducted in selected sites in parallel with Module 1. During periods of parallel enrolment, patient entry into Module 1 will be prioritised at sites conducting both Module 1 and Module 2 of this protocol.

The schedule in Cycle 1 involves dose ramp-up in from a starting dose of AZD0466 on Day 1 (one quarter of the target dose), with subsequent titration to the intermediate dose on Day 4 (one half of the target dose), and to the target dose on Day 8. Patients will receive a loading dosage of oral voriconazole followed by maintenance dosing in Cycle 1, as specified in the prescribing information for voriconazole (Voriconazole Prescribing Information). The dose of AZD0466 administered in combination with voriconazole will be one quarter of the target dose, to mitigate against a potential increase in exposure to the active moiety AZD4320 if a DDI exists between AZD0466 and voriconazole.

A visual representation of the DDI component of Module 2 (Cycle 1) is shown in [Figure 2](#).

Figure 2 Schema for Cycle 1 of Module 2

* The target dose (TD) of AZD0466 is the highest dose level determined as tolerated by the SRC in Part A of Module 1 at the point of first patient enrolment in Module 2.

**After reaching AZD0466 TD at D8 there will be a dose reduction on D15 to the D1 equivalent dose, with a return to full TD at the next AZD0466 administration day.

*** Voriconazole administration will be discontinued on Day 19 after collection of the last PK blood sample.

BID, twice a day; D, Day; IV, intravenous; PK, pharmacokinetic; PO, by mouth; RU1: first ramp-up dose; RU2: second ramp-up dose; SRC, Safety Review Committee; TD, target dose.

A minimum of 10 and up to 14 patients overall will be enrolled at selected sites to investigate the potential DDI between AZD0466 and voriconazole.

The DDI part of Module 2 (Cycle 1) will be performed in 3 periods over 21 days, as follows:

Period 1 (Days 1-10): AZD0466 infusion on Days 1, 4, and 8

Period 2 (Days 11-14): Voriconazole administration bid

Period 3 (Days 15-21): AZD0466 infusion (at the Day 1 equivalent dose) on Day 15 in combination with voriconazole bid on Days 15-19.

Module 2 Cycle 1 (DDI Part) will utilise a target dose of AZD0466 that has been declared tolerable in the dose escalation Part A of Module 1 (Table 22 in the study protocol). After reaching the target dose at Day 8, there will be a dose reduction at Day 15 to the Day 1 equivalent dose, and thereafter there will be a return to the full target dose.

In Module 2 Cycle 2 (after the DDI part), patients may receive AZD0466 as monotherapy at a higher target dose, if a new higher AZD0466 dose level was declared tolerable in Module 1. This dose increase may be implemented without a dose ramp up. This will allow patients to continue to receive study treatment at a tolerated dose within the predicted efficacious dose range in humans, see study protocol Section 11.1.3.1.

In Cycle 1, patients will be admitted as inpatients for 36 hours on Days 1-2, 4-5, 8-9, and overnight on Day 15. Additional inpatient admission days will be at the Investigator's discretion. During Period 2, voriconazole administration will occur on an outpatient basis.

The SoA for the DDI part (Cycle 1) of Module 2, including PK sampling times, is provided in Tables 21, 22 in the study protocol.

The SRC may assess safety data from Module 2 that could affect the conduct of Module 1.

11.2 Endpoints and Associated Variables

11.2.1 Efficacy Variables

For the definitions of the efficacy variables for the response evaluation criteria variables for ALL and AML, and extramedullary disease refer to the Section 3.2.1.

11.2.1.1 Peripheral Blood

Peripheral blood will be collected for complete blood count (CBC) (laboratory safety assessment) as indicated in the SoA in Tables 21, 22 in the study protocol. **CC1**

11.2.1.2 Extramedullary Disease

Refer to Sections 3.2.1.2.

11.2.1.3 Bone Marrow

Bone marrow core biopsy and bone marrow aspirate should be performed as specified in the SoA

in Tables 25, 26 in the study protocol.

- Screening (between Day -28 and -1)
- Cycle 2 Day 16 or 17
- Cycle 3 and subsequent cycles between Day 23 to 28
- Disease progression or EoT visit

The disease progression sample collection may occur at the safety follow-up visit (if conducted in person) if not collected previously. Additional bone marrow or peripheral blood samples may be collected, as clinically indicated.

